Additionally, A Data and Safety Monitoring Board (DSMB), consisting of at least 2 clinicians and one biostatistician not directly involved in the study (Table 1). The DSMB will review SAEs every six months during the study. The DSMB will be provided with unblinded data from the study so as to examine whether the study should be stopped because the study interventions are either clearly beneficial or harmful to participants. In addition to IRB, the Chairman of DSMB will be informed of any serious adverse events occurring during the study. If at any time during the study, more than 40% of the patients in the active treatment arm of the study have had a serious adverse event, the study will be stopped. The primary concern of the investigators of this study is the safety of the participants.

Members of DSMB will include the following clinicians and biostatistician:

Table 1. Data Safety Monitoring Board

Member Name	Specialty	Institution
[name] (Chairperson)	Psychiatry, Child and Adolescent Psychiatry, Clinical Research	Massachusetts General Hospital, Boston
[name]	Psychiatry, Child and Adolescent Psychiatry, Clinical Research	Massachusetts General Hospital, Boston
[name]	Psychology, Clinical Research, Statistician	Massachusetts General Hospital

Reporting Procedures for All Adverse Events

After review with the subject by the study site personnel, all Adverse Events occurring during the study, whether or not attributed to the Niraxx device or tPBM procedure, observed by the Investigator or reported by the subject, will be documented in the subject's source document and on the appropriate CRF pages. The following attributes must be assigned:

- Description of event
- Date of onset
- Date of resolution (if applicable)
- Seriousness
- Relationship to the study device and/or procedure(s)
- Intensity
- Action(s) taken
- Outcome(s)

Intensity is defined as a measure of the severity of a reaction, effect or experience. The measurement(s) are described as mild, moderate or severe. The event itself, however, may be of relative minor medical significance.

The intensity of Adverse Events is assessed as mild, moderate or severe according to the following index scale:

- **Mild.** The Adverse Event is transient, requires no treatment, and does not interfere with the subject's daily activity.
- **Moderate.** The Adverse Event introduces a low level of inconvenience or concern to the subject and may interfere with daily activities, but is usually ameliorated by simple therapeutic measures.
- **Severe.** The Adverse Event interrupts the subject's usual daily activity and requires systematic therapy or other treatment.

If the Adverse Event is of such intensity in the Investigator's judgment that it warrants withdrawal from the study, the subject should be withdrawn from treatment. The subject should be given appropriate care under medical supervision until symptoms resolve.

The relationship of an Adverse Event to the study device or procedure will be graded as follows:

- **Unrelated.** The Adverse Event is not associated with the study device use.
- **Possible.** This causal relationship is assigned when the Adverse Event:
 - Follows a reasonable temporal sequence from device use,
 - Could have been produced by the subject's clinical state or other modes of therapy administered to the subject, or
 - Cannot be reasonably explained by known characteristics of the subject's clinical state.
- **Definite.** This causal relationship is assigned when the Adverse Event:
 - Follows a reasonable temporal sequence from device use;
 - Abates upon discontinuation of the treatment; and
 - Is confirmed by the reappearance of the Adverse Event on repeat exposure.

Serious Adverse Events

All Serious Adverse Events must be reported to the overseeing Institutional Review Board (IRB) and Niraxx, Inc as required.

If the Investigators are notified by Niraxx, Inc or its designee of any Serious Adverse Events that are considered to be Unanticipated Adverse Device Effects, the Investigators must notify his/her own IRB/EC as required.

Deaths

Deaths which must be reported to Niraxx Inc include all deaths while participating the study.

Withdrawals for Adverse Events

All Adverse Events which result in the subject's withdrawal from the study must be reported immediately by telephone to Niraxx Inc.

The Investigator may be asked to provide detailed follow-up information. The Investigator will determine the reportability of the event on a case-by-case basis, and will report to the appropriate regulatory authorities evaluating the study device as necessary.

11. Privacy and Confidentiality

- Study procedures will be conducted in a private setting
- Only data and/or specimens necessary for the conduct of the study will be collected

Mass General Brigham Institutional Review Board
Intervention/Interaction Detailed Protocol

- Data collected (paper and/or electronic) will be maintained in a secure location with appropriate protections such as password protection, encryption, physical security measures (locked files/areas)
- Specimens collected will be maintained in a secure location with appropriate protections (e.g. locked storage spaces, laboratory areas)
- Data and specimens will only be shared with individuals who are members of the IRB-approved research team or approved for sharing as described in this IRB protocol
- Data and/or specimens requiring transportation from one location or electronic space to another will be transported only in a secure manner (e.g. encrypted files, password protection, using chain-of-custody procedures, etc.)
- All electronic communication with participants will comply with Mass General Brigham secure communication policies
- Identifiers will be coded or removed as soon as feasible and access to files linking identifiers with coded data or specimens will be limited to the minimal necessary members of the research team required to conduct the research
- All staff are trained on and will follow the Mass General Brigham policies and procedures for maintaining appropriate confidentiality of research data and specimens
- The PI will ensure that all staff implement and follow any Research Information Service Office (RISO) requirements for this research
- Additional privacy and/or confidentiality protections

12. References

Achenbach, T. M., & Rescorla, L. A. (2003). *Manual for ASEBA Adult Forms & Profiles*. Burlington, VT: University of Vermont, Research Center for Children, Youth, & Families.

Adler, L. A., Spencer, T., Faraone, S. V., Kessler, R. C., Howes, M. J., Biederman, J., & Secnik, K. (2006). Validity of pilot adult ADHD self report scale (ASRS) to rate adult ADHD symptoms. *Ann Clin Psychiatry*, 18(3), 145-148. doi:10.1080/10401230600801077

American Psychiatric Association. (2013). *Diagnostic and statistical manual of mental disorders (5th ed.)* (5th ed.). Arlington, VA: American Psychiatric Publishing.

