The purpose of this 8-week double-blind randomized placebo-controlled study is to assess the tolerability, safety, and efficacy of tPBM in adult patients with ASD. Based on our central hypothesis that tPBM will be safe, tolerable, and effective in improving ASD symptoms in adults, we propose to enroll up to 27 participants of both genders ages 18-50 years with intact intellectual functions satisfying DSM-5 criteria for ASD.

Primary Aims:

Aim 1. To examine the clinical efficacy and safety of tPBM in patients with ASD. We will study the short- and long-term clinical effects of tPBM in 27 adults with ASD by conducting an 8-week randomized clinical trial (RCT).

Secondary Aim:

Aim 1. Explore anti-inflammatory biomarker response to tPBM treatment. We will examine any relationship to ASD symptom severity before and after the 8-week treatment course.

Aim 2. To study the treatment effect of tPBM on mood, social cognition, executive function, ADHD, depression and anxiety symptoms in adults with ASD.

3. General Description of Study Design

This study is a double-blind, placebo-controlled, sequenced parallel study on the use of tPBM as treatment for ASD symptoms in adult patients. This study will last up to 12 weeks from enrollment (allowing up to four weeks from the date of consent to schedule and complete the initial screening process).

4. Subject Selection

Subjects diagnosed with ASD who meet all inclusion criteria, have none of the exclusion criteria, and are willing to undergo the Informed Consent process will be eligible to participate in this clinical study.

Inclusion Criteria

Subjects may be included in the study only if they meet all of the following criteria:

- Male or female participants between 18 and 50 years of age (inclusive)
- Fulfills DSM-5 diagnostic criteria for autism spectrum disorder as established by the clinical diagnostic interview.
- Participants with at least moderately severity of ASD symptoms as demonstrated by SRS raw score ≥ 85 and CGI-ASD severity score ≥ 4

- Participants must understand the nature of the study. Participants must be deemed not to have impaired decision-making capacity and must have the capacity to provide direct informed consent. Participants must sign an IRB-approved informed consent form before initiation of any study procedures.

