Individuals who express interest in the study, will be screened for eligibility by the study coordinator or a research assistant via phone. If their answers to the IRB approved phone screen indicate that they may be eligible for the study, the potential subject will be asked to complete the Social Responsiveness Scale – Second Edition (SRS-2) online via RedCap, a secure online data capture system. The study coordinator will send a link to complete the SRS-2 electronically to the participant via REDCap. An online consent statement will appear, prompting participant to indicate their agreement to participate in the online questionnaire portion of the study. If the participant indicates their agreement, the data capture system will proceed to the SRS-2. After completing the SRS-2, eligible participants based on inclusion and exclusion criteria will either be scheduled to speak with a study clinician via phone to obtain informed consent (and assent as necessary) prior to completing further screening and baseline study procedures via virtual visit. If an additional family member of the subject is available, we will ask that family member to independently complete an SRS-2 form following the same pre-screening procedure. Both forms will be scored and the form with the higher score will be used to determine subject eligibility in order to reduce the possibility of under-recognition of social impairment.

Informed consent will be obtained remotely prior to administration of any study related procedures. If a subject expresses interest in the study, the study staff will send the consent form to subjects in PDF form ready for Adobe eSignature via email with a brief statement (email temple submitted) explaining

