- Concomitant Medications
- CGIs
- GAF
- SRS-2 (Pre-Screening)

- ABCL
- MGH-SECS-C
- MGH-SECS-I

Study participants may request the results of their scales and assessments. In this case, the subject will receive a letter providing a basic interpretation of the results and will be available for any questions or concerns.

Washout Period

After the screening period, subjects who are currently taking prohibited medications as noted in exclusion criteria, and willing to discontinue the use of their medication may do so in order to be eligible for participation in this study, if clinically appropriate per clinician judgment. If appropriate, medication washout will be recommended by our clinicians to participants and current providers. Clinicians will determine a washout schedule based on the half-life of the medication, the adverse effects associated with treatment and withdrawal, and an assessment of individual factors including duration on drug and dose. No subjects will be asked to discontinue ongoing exclusionary medications to participate in the study; however, if the subject is already tapering the medication off for clinical reasons at the time of screening and evaluation for participation, they will be considered eligible to participate only after the washout period as described. Our office does not take over care for the patient, but remains available during this time period. The washout schedule will be discussed with the participant and current providers.

Study Treatment Phase (Weeks 0-8)

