Pregnancy potential will be monitored at screening, baseline, Week 2, Week 4, and Week 6 by a clinician-rated reproductive potential form. If, during any of these visits the participant is deemed to have pregnancy potential, a member of study staff will contact the participant to complete a phone screen to ensure the participant understands why a urine pregnancy test is necessary, explain the required procedures, and obtain verbal consent from the subject to send the urine pregnancy test to their home address. If the participant provide verbal consent, a pregnancy test will be overnight shipped using study funds and sent directly to the subject's home address within 24 hours. The participant will be asked to stop treatment until the urine pregnancy test is performed. In addition, a phone call will be set up at a specified time the next day. During this call, the study coordinator will review the procedure for completing the urine pregnancy test while on the phone and have the subject complete the test while remaining on the line. The subject will verbally report the result to the study coordinator, and will also send visual confirmation (i.e. a photo of the test with results send via secure email) prior to continuing the study treatment. If the participant decides that they no longer feel comfortable completing the urine pregnancy test, they will be withdrawn from the study.

Subjects will be instructed to administer the treatment sessions daily for eight weeks, with each session lasting 20-50 minutes. Subjects will be instructed to contact the investigator or a member of his staff at any time between visits concerning adverse events or worsening of symptoms.

Baseline Visit (Week 0)

The overall baseline session is estimated to last about 60 minutes. The subject will be examined to inspect the sites of application (left and right forehead) for any possible skin lesions (e.g. laceration or signs of inflammation) which would contraindicate the treatment. The site of the test treatment will also be examined. The subject will then be instructed on the appropriate administration of tPBM.

Following assessments will be performed at the Baseline Visit:

- Virtual examination of exposure sites
- Urine pregnancy test (females only)
- Pregnancy potential monitoring form
- CGIs
- GAF
- CTAE
- Concomitant Medications
- Ham-A
- Ham-D
- AISRS
- BRIEF-A
- ASRS
- Q-LES-Q

Study Treatment: Virtual Clinical Monitoring Visits (Weeks 1-6)

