- MGH Social-Emotional Competence Scale [Clinician-Rated Measure] (MGH-SECS-C): This is a 37-item scale that assesses change in the frequency and severity of core and associated symptoms of ASD.
- Adult ADHD Investigator Symptom Report Scale (AISRS;(Spencer et al., 2010)): The AISRS, shown to be sensitive to drug effects in adult populations, assesses each of the 18 individual criteria symptoms of ADHD in DSM-IV on a severity grid (0=not present; 3=severe; overall minimum score=0; maximum score=54).
- Hamilton Anxiety Scale (HAM-A; (M Hamilton, 1959)): a rating scale used to assess anxiety. This questionnaire consists of 14 questions assessing these symptoms. Clinicians are asked to rate each symptom as absent, mild, moderate, severe, or very severe.
- Hamilton Depression Scale (HAM-D; [(M. Hamilton, 1960))]: a rating scale used to assess depression. This is a multiple-item questionnaire used to rate the severity of depression in adults. Clinicians are asked to rate each symptom as absent, mild/trivial, moderate or severe.

Clinician-Rated Safety Measures

(Administered at baseline, all treatment visits and at final visit)

- Clinician-Rated Treatment Emergent Adverse Events Log (CTAE): to record any spontaneous adverse health events experienced during the study, along with duration, severity, cause, treatment, and outcome.
- Concomitant Medications: to record additional medications taken during the study.

Subject-Rated Measures

Subject-Rated Behavioral Measures

(Administered at screening evaluation)

- Demographic Interview: This brief interview will collect information regarding socioeconomic status and history of head injury or trauma (Hollingshead, 1975).

(Administered at baseline, midpoint, and final study visits)

- Social Responsiveness Scale-Second Edition Self-Report (SRS-2; (Constantino & Gruber, 2012)): a 65-item rating scale completed by subjects that is used to measure the severity of autism spectrum symptoms as they occur in natural settings.
- Adult ADHD Self-Report Scale (ASRS; (Adler et al., 2006)): The 18-item ADHD Rating Scale will be completed to evaluate frequency of ADHD symptoms on a scale of 0 to 4.
- Behavior Rating Inventory of Executive Function-Adult Self-Report Version (BRIEF-A; (Roth, Isquith, & Gioia, 2004)): a 78-item rating scale to assess level of executive function deficits.

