Primary outcome measure of efficacy will be reduction in ASD symptoms as measured by change from baseline on the clinician-rated SRS-2. Responders will be defined as those who demonstrate a $\geq 25\%$ reduction in SRS-2 total score *and* a score of 2 or 1 on the CGI-ASD-Improvement subscale ("much" or "very much improved").

Secondary outcome measure:

1. Treatment-related changes in associated psychopathology, social cognition, executive functions will be assessed by:
 - MGH Social-Emotional Competence Scale (MGH-SEC Scale; clinician- & observer-rated)

- Social Responsiveness Scale-Second Edition (SRS-2; self- & observer-rated)
- Adult Behavior Checklist (ABCL; self- & observer-rated)
- Behavior Rating Inventory of Executive Function-Adult Self Report Version (BRIEF-A) or parent version (BRIEF-P) for youth
- Adult ADHD Self-Report Scale (ASRS) & clinician-rated Adult ADHD Investigator Symptom Report Scale (AISRS) and CGI-ADHD scale
- Quality of Life Enjoyment and Satisfaction Questionnaire (Q-LES-Q)
- Hamilton Anxiety scale (HAM-A) & clinician-rated CGI-Anxiety scale
- Hamilton Depression scale (HAM-D) & clinician-rated CGI-Depression scale

2. Safety and tolerability will be assessed by:

- The monitoring of spontaneous treatment-emergent adverse events with the Clinician-rated Treatment-emergent Adverse Events Log (CTAE)
- tPBM Self-Report Questionnaire (TSRQ)

SAFETY

Consistent with good clinical practice, safety will be monitored at each study visit by a subject's assigned clinician. This clinician will be available 24 hours a day by page. The principal investigator will supervise all study activities including ratings and reported adverse events. All procedures have been designed to minimize subject discomfort, and no subject will be asked to engage in research procedures not outlined in the consent form.

If study participation is discontinued due to safety reasons, participants will receive three follow-up visits, giving adequate time for appropriate psychiatric care to be arranged.

Study Treatment

Safety will be monitored through treatment-emergent adverse events and subject rated TSRQ responses. Subjects will be monitored for adverse events at each visit. All adverse events will be recorded. A subject may be dropped from the study or dosage may be decreased at any time due to adverse events. All adverse events will be reported to the PHRC according to PHRC guidelines. All concomitant medications will be assessed at every study visit.

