Appendix B

Table II. Study Schema

Weeks	99	0	1	2	3	4	6	8
Visits	Screen	Baseline	W1	W2	W3	MP	W6	EP/ ET
Informed Consent	X							
tPBM Test Dose								
tPBM Device Subject Training		X						
tPBM Initial Titration:			X					
Day 1-3, 20 min/day								
Day 4-7, 30 min/ day								
tPBM Treatment - 40 min/day			X					
tPBM Treatment - 50 min/day				X	X	X	X	X
Diagnostic Assessments								
Inclusion/Exclusion Criteria	X							
Psychiatric Evaluation & Medical History	X							
Physiological Procedures								
Virtual Examination of Exposure Sites		X	X	X	X	X	X	X
Urine pregnancy test	X*	X*	X*	X*	X*	X*	X*	
Clinician-Rated Assessments								
Pregnancy Potential/Monitoring Form	X	X		X		X	X	
MGH-SECS-C	X					X		X
AISRS		X				X		X
HAM-A		X				X		X
HAM-D		X				X		X
CGIs	X	X	X	X	X	X	X	X
CTAE		X	X	X	X	X	X	X
Concomitant Medications	X	X	X	X	X	X	X	X
GAF	X	X	X	X	X	X	X	X
Progress Note		X	X	X	X	X	X	X
Subject-Rated Assessments								
Demographic Interview	X							
SRS-2	X					X		X
ASRS		X				X		X
BRIEF-A		X				X		X
Q-LES-Q		X				X		X
TSRQ			X	X	X	X	X	X
Observer-Rated Assessments								
SRS-2	X							X
MGH-SECS-I	X							X
ABCL	X							X

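### The SRS-2, the scale behind the primary change score, is not scheduled at Week 0, so its baseline is the earlier eligibility score, which for a washout subject predates the end of washout

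*Combined protocol and SAP*

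**What the plan says.** The primary outcome (section 6, Data Analysis) is "reduction in ASD symptoms as measured by change from baseline on the clinician-rated SRS-2". A responder needs both a 25% fall in the SRS-2 total and a CGI-ASD-Improvement score of 1 or 2.

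The SRS-2 is first completed online, before the consent call. Section 5 says: "After completing the SRS-2, eligible participants based on inclusion and exclusion criteria will either be scheduled to speak with a study clinician". The screening list in section 6 carries it with the label Pre-Screening. The Week 0 list, introduced by "Following assessments will be performed at the Baseline Visit", has 13 items and no SRS-2. The Week 4 and Week 8 lists include it. Table II (Appendix B) agrees: under "Subject-Rated Assessments" the SRS-2 is marked at Weeks 99, 4 and 8, and the observer-rated SRS-2 at Weeks 99 and 8.

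Two other places point to a later baseline. The heading over the self-report SRS-2 in the scale descriptions reads "Administered at baseline, midpoint, and final study visits", and section 9 refers to a baseline before treatment starts without naming a visit.

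On medication, the Washout Period paragraph begins "After the screening period, subjects who are currently taking prohibited medications as noted in exclusion criteria, and willing to discontinue" and allows this where a clinician judges it appropriate. It also covers subjects already tapering at screening, who become eligible once washout is over. Section 3 sets the time frame, "allowing up to four weeks from the date of consent to schedule and complete the initial screening process", within a study of at most 12 weeks from enrollment.

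**The concern.** A change score should start from the subject's state just before treatment. On the two schedules that staff will work from, the SRS-2 starts instead from the score that decided eligibility. That applies to every subject. It is sharpest for anyone who stops a psychotropic, or finishes tapering one, after screening: the recorded baseline reflects the drug or the taper, while Weeks 4 and 8 reflect its absence. Their SRS-2 change then mixes the effect of stopping the drug with the effect of tPBM or sham, and no scheduled SRS-2 separates the two. A pre-treatment questionnaire that was not collected cannot be recovered later.

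The schedule also sits badly with the protocol's own aim of stable medication, which requires an unchanged psychotropic dose for four weeks before treatment and through the trial. AISRS, HAM-A, HAM-D, ASRS, BRIEF-A and Q-LES-Q are all taken at Week 0; the scale that carries the primary outcome is not.

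**Working it through.** The plan states no figure to reproduce: it gives no power, effect size or SD. The check is a reading of the schedules, followed by illustrative sizing.

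**1. Schedule.** SRS-2 assessments listed between the end of screening and the first session: 0. Rating-scale rows with a Week 99 mark and no Week 0 mark: 5 (subject SRS-2, observer SRS-2, MGH-SECS-C, MGH-SECS-I, ABCL). Scales first taken at Week 0: 6 (named above). If the screening list was meant to require a fresh SRS-2 at the screening visit, the order does not change, because washout follows screening.

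**2. Time from score to first session.** Consent to treatment: at most 4 × 7 = 28 days. Treatment: 8 × 7 = 56 days. Ratio 28/56 = 50%. Since 12 − 8 = 4 weeks, any washout after consent has to fit inside those 28 days. The interval between the online SRS-2 and consent has no stated limit, so the total has none either.

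**3. SRS-2 half of the responder rule.** At the entry minimum of 85 the required fall is 0.25 × 85 = 21.25 points, to a cut-off of 63.75. One point is 1/21.25 = 4.7% of that fall, and less at higher baselines. The 85 is the higher of the self and informant scores where both exist, so the form analyzed may start lower.

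Let S be the SRS-2 change caused by stopping the drug. The documents give neither its size nor its direction; the values here are assumptions. The reduction needed from the true pre-treatment score is (85 + S − 63.75)/(85 + S):

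| S | −10 | −5 | 0 | +5 | +10 |
|---|---|---|---|---|---|
| Reduction needed | 15.0% | 20.3% | 25.0% | 29.2% | 32.9% |

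**4. Between arms.** Suppose w of N subjects wash out, each shifts by S, and they fall at random into arms of n1 and n2. The expected gap between arm means is 0. With p = w/N, its SD is |S| × √[p(1 − p) × N/(N − 1) × (1/n1 + 1/n2)]. Section 6 gives up to 27 randomized (13 and 14); section 9 gives 54 (27 and 27).

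| N | w | SD at 5 points | SD at 10 points |
|---|---|---|---|
| 27 | 1 | 0.37 | 0.74 |
| 27 | 2 | 0.51 | 1.03 |
| 27 | 6 | 0.82 | 1.63 |
| 54 | 1 | 0.19 | 0.37 |
| 54 | 2 | 0.26 | 0.52 |
| 54 | 6 | 0.43 | 0.86 |

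For one or two subjects at N = 27, this is 0.37/21.25 = 1.7% to 1.03/21.25 = 4.8% of the responder threshold.

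**5. Small-number effects.** If one responder status did change, the arm's rate would move by 1/14 = 7.1 to 1/13 = 7.7 percentage points, or 1/27 = 3.7 with 27 per arm. Two washout subjects fall in the same arm with probability (13 × 12 + 14 × 13)/(27 × 26) = 338/702 = 0.48, or (2 × 27 × 26)/(54 × 53) = 1404/2862 = 0.49.

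**The case against.** *The scale description already says baseline.* It does, and ASRS, BRIEF-A and Q-LES-Q under the same heading are taken at Week 0. But the observer-scale heading also says baseline for measures that the opening of the assessment section and Table II place at Week 99, so the word is used loosely. Both working schedules omit Week 0. If Week 0 was intended, those schedules need the same correction.

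*The washout group may be empty.* This stands. Psychotropics are allowed on a stable dose, nobody is to be asked to stop one for the study, and the protocol gives no expected number. Light-activated drugs have their own 14-day rule. The case for a Week 0 score therefore rests on all subjects, with washout as the sharpest example.

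*The primary names a different form.* This also stands. Table II has only subject- and observer-rated SRS-2 rows, and the self- and observer-rated forms are listed as secondary outcomes. The rater has to be settled before a Week 0 score can be called the primary baseline.

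A reader might infer that stopping a drug could by itself make someone a responder. It could not: CGI-ASD-Improvement of 1 or 2 is also required, and CGIs are rated again at Week 0.

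A reader might also infer that unsuitable washout subjects can slip in, because Table II marks the eligibility check at Week 99 only. The documents do not support this as a material problem. Tapering subjects are eligible only after washout; the four-week dose rule is counted back from treatment start; CGIs, GAF, HAM-A, HAM-D and medications are reviewed at Week 0; and an ineligible subject can be removed. These safeguards do not, however, supply an SRS-2 total.

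**Conclusion.** The point holds as a scheduling gap that should be closed. No SRS-2 is listed at Week 0, so the only pre-treatment value is the selection score. For a subject who washes out after screening, that value was taken under different medication from all follow-up.

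The effect is added noise in the change score and in the SRS-2 half of the responder rule. With one or two washout subjects and assumed shifts of 5 to 10 points, the chance gap between arms has an SD of about 0.4 to 1.0 points at 27 randomized and 0.2 to 0.5 at 54. With no washout subjects, this component is zero.

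Systematic bias between arms is a tempting further step, but the documents do not support it. Section 6 randomizes on completion of consent, so a washout could follow assignment. Subjects and clinicians are blind, though, and no treatment has been given before Week 0, so stopping a drug in that interval should not depend on arm. This conclusion assumes the blind holds.

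Confidence is medium: the reading of the schedules is firm, while the number of subjects affected and the size of any shift are unknown.

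**What to change.** 1. Mark the SRS-2 at Week 0 in Table II and add it to the Week 0 list in section 6, for every subject, completed after any washout and before the first session. Doing this for all keeps baseline timing equal and agrees with the scale description.
2. State that the Week 0 score is the baseline for the change score and the 25% rule, and that the pre-screening score serves eligibility only.
3. Correct the primary outcome so that it names the SRS-2 form actually collected, and schedule that same form at Week 0.

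The cost is one online form, which section 6 puts at 5-10 minutes, in a Week 0 session of about 60 minutes, plus small edits to Table II, the visit list and the outcome definition. The price is slightly more burden at that visit.

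No added eligibility check or change to the exclusion wording is needed. Their effect on results would be negligible, and a check at Week 0 before randomization would not fit a trial that randomizes on consent and then mails the device.
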